The goal of this study is to conduct a small randomized control trial (RCT) to test the safety and preliminary efficacy of a novel combination therapy to treat acne vulgaris. We will also explore the effects of the treatments on psychosocial factors (Dermatology Life Quality Index (DLQI), social anxiety, depressive symptomatology, and self-esteem). The RCT will have 3 arms: 1) Standard treatment: photodynamic therapy with 5-aminolevulinic acid (ALA-PDT); 2) Microcurrent therapy (MCT); and 3) combination therapy (ALA-PDT + MCT). The main outcomes will be: 1) number of acne lesions; 2) amount of sebum produced, 3) degree of acne severity; and 4) improvement in dermatologic quality of life. The specific aims of the study are:

Aim 1: To examine the safety and preliminary efficacy of MCT for the treatment of acne vulgaris

Ho1: MCT will be as safe and effective as ALA-PDT in the treatment of acne vulgaris.

Aim 2: To examine the safety and preliminary efficacy of combination therapy (ALA-PDT + MCT) for the treatment of acne vulgaris

Ho2: Combination therapy (ALA-PDT + MCT) will be as safe and effective as ALA-PDT in the treatment of acne vulgaris.

Aim 3: To determine if combination therapy is a more effective treatment (fewer number of acne lesions, decreased amount of sebum produced, lesser degree of acne severity and greater improvement in dermatologic quality of life) for acne than either type of monotherapy.

Ho3a: Combination therapy (ALA-PDT + MCT) will be more effective than standard therapy in the treatment of acne vulgaris.

Ho3b: Combination therapy (ALA-PDT + MCT) will be more effective than MCT in the treatment of acne vulgaris.

Ho3c: Participants in the combination therapy arm will exhibit less side-effects than those in the standard treatment arm.

Aim 4: To explore the effects of the three therapeutic modalities on psychosocial factors (social anxiety, depressive symptomatology, and self-esteem).

Ho4: Participants in the combination therapy arm will report greater improvement in psychosocial factors than those in either monotherapy arm.

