efficacy of combination photodynamic therapy with 5-aminolevulinic acid and microcurrent therapy for the treatment of acne vulgaris. We will recruit up to 60 males and females and randomly assign them to one of 3 treatment arms (*photodynamic therapy with 5-aminolevulinic acid (ALA-PDT)*; *microcurrent therapy (MCT)*; and *combination therapy (ALA-PDT and MCT)*). (See Table 1.) All participants will complete a baseline assessment prior to initiating treatment and two follow-up assessments at 4 weeks and 12 weeks post termination of treatment. During the treatment phase, we will conduct intermediary assessments to help us track the progression of the treatment over time at weeks 3 and 5 as well as 1 week post the termination of the treatment (week 6). We will conduct both physiological and psychosocial assessments; the content of the intermediary assessment will be much less than the other 3 assessments to reduce participant data. The most comprehensive assessments will be conducted at baseline and the 2 follow-up points and will consist of all of the physiological and psychosocial factors as well as demographic factors that will be collected exclusively at the baseline assessment. At the intermediary assessments we will collect the number of acne lesions, amount of sebum produced and dermatologic quality of life. Psychosocial data will be collected via computer-assisted self-interviews (CASI). Physiological data will be entered into the computer program by research staff.

Table 1. Frequency and duration of study visits (assessment(s) and treatment(s))

	ALA-PDT	MCT	ALA-PDT+MCT
Week 1	✓	✓	✓+✓
Week 2		✓	✓
Week 3	✓	✓	✓+✓
Week 4		✓	✓
Week 5	✓	✓	✓+✓

12. Description of the ALA-PDT treatment arm

In this arm participants will receive 3 ALA-PDT treatments at 2 week intervals. The duration of each treatment will be approximately 2 hours. At each treatment, we will apply a formulation of ALA called Levulan® Kerastick (manufactured by Dusa Pharmaceuticals, MA, USA) to the affected areas of the participant's face (See Figure 2). After 1 hour incubation, the affected areas will be exposed to a light source using photodynamic machine between 15 to 20 minutes. (See Figure 2). Each treatment will take approximately 90 minutes. At the completion of each treatment session, participants will be counseled to follow the photo-protection measures.

Figure 2. Levulan® Kerastick and Photodynamic Therapy Machine*

[figure not shown]

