*<http://www.dermacaremedical.com/acne-treatment.php>

13. Description of the MCT treatment arm

In this arm participants will receive 5 MCT treatments at 1 week intervals using MCT machine (See Figure 3). The duration of each treatment will be approximately 45 minutes. Trained staff will place one electrode in one of the regional areas of the lymph nodes or affected area (i.e. the forehead) and move the second electrode systematically from the affected area towards the stationary electrode. Once the entire affected area has been covered, the staff will move the first electrode to another regional area of the lymph nodes or affected area and the process will be repeated. This will continue until all of the affected areas have been treated.

Figure 3. Microcurrent Therapy Machine* and Application in a Cosmetic Procedure**

*<http://www.laserbodyandskincare.com/product.php?productid=17517>

**<http://labeledlula.com/microcurrent-therapy>

14. Description of the combination (ALA-PDT + MCT) treatment arm

In this arm participants will receive 3 ALA-PDT treatments at 2 weeks intervals and 5 MCT treatments at 1 week intervals. At week 1, 3 and 5 participants will receive MCT treatment as described in 13 followed by ALA-PDT treatment as described in 12. These visits will last approximately 135 minutes. In weeks 2 and 4, participants will only receive MCT treatment as described in 13.

15. Assignment to Treatment Conditions

Using block randomization procedures, we will randomize participants into the three conditions in blocks of 6 using a computerized randomization program. The data manager will prepare a set of sealed envelopes containing the condition assignment as determined by the randomization program and place the envelopes into a box in sequential order. The box will be stored in a secure place accessible only to the research staff enrolling participants. After obtaining informed consent and completing the enrollment procedures, staff will remove the first envelop from the box to ascertain the condition assignment of the newly enrolled participant. We have used these procedures successfully in a number of previous studies. We will monitor the randomization procedures and adjust if necessary to ensure equivalence in the number of participants assigned to each condition.

16. Assessment Procedures

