Some participants may experience postinflammatory hyperpigmentation, pain and burning sensation as a result of being treated with ALA-PDT, but these side-effects occur rarely and when they do they are typically associated with longer incubation periods of 3 hours or longer. To minimize this risk, we are proposing to use 1 hour incubation period, the shortest time possible to obtain the desired sensitization. Consequently, we consider the risk level for this concern is of low magnitude and duration. Individuals treated with ALA-PTA will experience short-term sensitivity to sunlight. This risk is minimized by the brief incubation period we selected and the careful instructions we will provide to participants regarding the need to protect themselves from exposure to sunlight. Thus, the risk is of low magnitude and duration.

Some participants may temporarily experience fatigue, nausea, sleepiness and flu-like symptoms 60 to 90 minutes after MCT, similar but slightly stronger than those that some people experience after a massage. Although these side-effects rarely occur, they are the by-product of the lymphatic system flushing toxins from the body and they resolve within 24 hours. To minimize this risk, we will strongly encourage participants to stay maximally hydrated to mitigate this side-effect. Thus, the risk is of low magnitude and duration.

Some participants may experience psychological distress from responding to some of the questions in our assessment battery. They may be sensitive about reporting their feelings regarding how acne affects their daily activities and social interactions or how sad, anxious or depressed they feel as a result. We have taken steps to minimize this risk by ensuring that our research staff is well trained and prepared to identify distress in our participants. Our staff will remind participants that they have the option of refusing to continue with the treatment or not answer any question that makes them feel uncomfortable or anxious. The risk level for this concern is of low magnitude and duration.

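### Side-effects are compared between arms, but no scheduled assessment asks about them, so the counts would rest on unsolicited reports at 5 contacts after session 1 in Arm 1 against 7 in Arms 2 and 3

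*Combined protocol and SAP*

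**What the plan says.** **Hypotheses.** Under the aims of the research protocol, Ho1 holds that MCT matches ALA-PDT on safety as well as efficacy, and Ho2 says the same of the combination. Ho3c is directional: "Participants in the combination therapy arm will exhibit less side-effects than those in the standard treatment arm".

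**Treatment visits.** Section 12, Arm 1: "In this arm participants will receive 3 ALA-PDT treatments at 2 week intervals". Section 13, Arm 2: "In this arm participants will receive 5 MCT treatments at 1 week intervals using MCT machine". Section 14, Arm 3: "In this arm participants will receive 3 ALA-PDT treatments at 2 weeks intervals and 5 MCT treatments at 1 week intervals". Within Arm 3, "At week 1, 3 and 5 participants will receive MCT treatment as described in 13 followed by ALA-PDT treatment as described in 12", and "These visits will last approximately 135 minutes". For the other weeks: "In weeks 2 and 4, participants will only receive MCT treatment as described in 13".

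**Assessments.** Every arm has the same schedule: baseline, weeks 3, 5 and 6, and two follow-ups (IRB form, section 2.C Part 3; protocol section 16, Table 2). Assessments precede that day's treatment. The intermediary ones cover lesion count, sebum and dermatologic quality of life. Baseline and follow-up add severity, social anxiety, depressive symptoms and self-esteem. The instruments in section 2.C Part 4 serve these outcomes; none is described as recording side-effects.

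**Safety.** Section K: "Some participants may temporarily experience fatigue, nausea, sleepiness and flu-like symptoms 60 to 90 minutes after MCT". It adds that these symptoms clear within 24 hours. The analysis plan (section 18; form section 3.M) promises only a descriptive presentation of safety information. Form section 3.P refers adverse event reporting to an institutional policy that is not reproduced.

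**The concern.** A between-arm comparison of side-effects needs the same question, asked at the same times, in each arm. The plan sets neither. Reports would surface when a participant happens to mention something or staff happen to notice it, and the opportunities for that are unequal. Arms 2 and 3 attend in weeks 2 and 4; Arm 1 does not. A difference between arms would then mix treatment effect with opportunity to report.

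The obvious repair, a side-effect form at every visit, would carry the same imbalance into the data. Nor can analysts recover afterwards what nobody asked. The results are meant to inform a decision on a larger trial, so a distorted safety signal matters in either direction.

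**Working it through.** **1. Contacts after the first session.** Take every week with a treatment (sections 12 to 14, Table 1) or an assessment (Table 2), and drop week 1.

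| Arm | Contacts | Number |
|---|---|---|
| 1 | weeks 3, 5, 6, Follow-up I, Follow-up II | 5 |
| 2 and 3 | weeks 2, 3, 4, 5, 6, Follow-up I, Follow-up II | 7 |

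The ratio is 7/5 = 1.4. Through week 6 the counts are 3 v 5. Scheduled assessments after week 1 are equal (5 in each arm), so the whole difference is the two treatment-only visits. The documents place the follow-ups at weeks 7 and 12 (form), weeks 9 and 12 (Table 2), or 4 and 12 weeks after treatment (section II), which is weeks 5 + 4 = 9 and 5 + 12 = 17. The 5 v 7 count is the same under all three.

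**2. Length of the combined visit.** MCT 45 minutes plus ALA-PDT 90 minutes gives 135, the stated figure. Section 12 also gives about 2 hours for ALA-PDT; 45 + 120 = 165 does not reproduce it.

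**3. Where the MCT reaction window falls.** Assume participants leave when the session ends, since no later observation is described. An MCT-only visit ends at minute 45.

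- Timed from the end of MCT, the window is minutes 45 + 60 = 105 to 45 + 90 = 135.
- Timed from the start of MCT, it is minutes 60 to 90.

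Either way it lies after an MCT-only visit and within a combined visit of 135 (or 165) minutes. Timed from the end, it closes just as the 135-minute visit does. The window is therefore in clinic at 0 of 5 Arm 2 sessions and 3 of 5 Arm 3 sessions (weeks 1, 3 and 5). In weeks 2 and 4, Arm 3 has the same 45-minute visit as Arm 2.

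**4. Session time.** Using the 90-minute ALA-PDT figure:

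- Arm 1: 3 × 90 = 270 minutes
- Arm 2: 5 × 45 = 225 minutes
- Arm 3: 3 × 135 + 2 × 45 = 495 minutes

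Arm 3 has both more contacts and more clinic time than Arm 1. Arm 2 has more contacts but less time.

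**5. Illustration.** If each contact independently yields a report with probability p, the chance of at least one report over k contacts is 1 − (1 − p)^k. The documents give no p.

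| Assumed p | k = 5 | k = 7 | Ratio |
|---|---|---|---|
| 0.02 | 9.6% | 13.2% | 1.37 |
| 0.05 | 22.6% | 30.2% | 1.33 |
| 0.10 | 41.0% | 52.2% | 1.27 |
| 0.20 | 67.2% | 79.0% | 1.18 |

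**6. Do the shared assessments cover every session?** Yes. Week 3, before treatment, covers the sessions of weeks 1 and 2; week 5 covers weeks 3 and 4; week 6 covers week 5.

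**The case against.** The best defence is that scheduled assessments are identical across arms, so unequal ascertainment is a possible consequence of a gap rather than something the plan prescribes. This stands as a limit: the documented fault is the missing common collection schedule. It does not remove the point, because following the plan as written leaves only unsolicited reports, and the contacts at which they can arise are unequal.

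Other objections also have force.

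- **The illustration builds in its result.** Giving every contact its own chance of a report means more contacts must yield more reports. If each contact covered the time since the last, extra contacts would mainly affect recall. Weeks 2 and 4 are also extra MCT sessions, so events there may be real treatment effects.
- **For Ho3c the tilt is conservative.** Extra reports in Arm 3 work against the hypothesis and could not create a false favourable result. For Ho2, however, they could make the combination look less safe than it is.
- **Reactions can be recalled.** They may last up to 24 hours, and Arm 2 returns weekly. That equalises the arms only if all are asked the same thing over the same period.

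A reader might infer that Arm 3 is always in clinic when MCT reactions begin, or that the same symptom is seen in Arm 3 and missed in Arm 2. The documents support neither: the first fails in weeks 2 and 4, and the second ignores later reporting. Nor does any named side-effect hypothesis compare Arm 2 with Arm 3.

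**Conclusion.** The point holds in this form and should be settled before enrolment. Three hypotheses compare side-effects, no scheduled assessment or listed instrument is described as collecting them, and the contacts at which reports could arise after session 1 are 5 in Arm 1 against 7 in Arms 2 and 3.

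More contacts would tend to raise the Arm 3 count in Ho2 and Ho3c. For Ho1 the net direction is unknown: Arm 2 has two more contacts than Arm 1, but less session time, and its expected reactions begin after participants have left. It would be wrong to conclude that the bias favours MCT alone. The 0 of 5 v 3 of 5 contrast between Arms 2 and 3 bears on the descriptive safety results only.

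No percentage here estimates a bias. The figures assume independent contacts and a report probability that the documents do not supply. The window result further assumes departure at the end of the session.

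**What to change.** - **Collection.** Add one identical side-effect question to the assessments that all arms share (weeks 3, 5, 6 and both follow-ups). It should cover the whole time since the previous shared assessment, including the 24 hours after each session. It can go into the computer self-interview already planned.
- **Analysis.** Base the between-arm side-effect comparison on those answers.
- **Other events.** Keep recording everything seen at any other contact, and report it in full by arm beside the number of sessions and contacts. Dropping directly observed events would be hard to defend in a study with a safety aim, and the recall question would bring many of them back.
- **Incubation.** Apply one rule to events during ALA incubation in Arms 1 and 3. Both have the same 1-hour incubation, so setting aside only Arm 3's events would favour the combination in Ho3c.
- **Reconcile.** The sponsor should reconcile the three sets of follow-up dates and the two ALA-PDT session lengths. In step 4 of form section 2.C Part 3, the cross-references to 3a and 3b are swapped relative to the treatments they name.

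The cost is a few minutes at visits already planned. The downside is recall: about two weeks during treatment and longer between follow-ups (12 − 9 = 3, 12 − 7 = 5 or 17 − 9 = 8 weeks, depending on the dates adopted). Recall is also not fully equal: before weeks 3 and 5 the latest session is two weeks back in Arm 1 but one week back in Arms 2 and 3. The report should say so.

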Amount of Sebum Produced. We will use the Sebumeter® SM 815 manufactured by CK Electronic to estimate the amount of sebum. The measurement is based on grease spot photometry. The mat tape of the Sebumeter® SM 815 is brought into contact with facial skin. It becomes transparent in relation to the sebum on the surface of the measurement area. Then the tape is inserted into the aperture of the device and the transparency is measured by a photocell. The light transmission represents the sebum content. <http://www.courage-khazaka.de/index.php/en/products/scientific/129-sebumeter>

Acne Severity. We will use the acne counts and the digital photographs of the affected areas to compute the acne severity level following the procedures established by Hayashi et al. (2008). We will not print the digital photographs. Trained research staff will visually inspect the digital photographs and assign a preliminary severity score to each half of the face using the following classification guide: 0–5 papules and/pustules for mild acne; 6–20 for moderate acne, 21–50 for severe acne; and more than 50 for very severe. Staff will examine each half of the face separately. The most severe classification obtained for either side of the face will be the assigned severity score.

J2. Psychosocial assessment

Demographic Variables. Participants will report their age, gender, race/ethnicity, education, employment, income, and zip code.

Dermatologic Quality of Life. We will use the Dermatology Life Quality Index (DLQI) developed by A. Y. Finlay and G. K. Khan (1992), one of the most widely used, dermatologic specific quality of life measures in the published literature to assess quality of life. The DLQI consists of 10 Likert type items; 9 of these items have 4 response categories scored from 0 to 3 with “very much” being “3” to “not at all” being “0”. Item 7 “*Over the last week, has your skin prevented you from working or studying*” uses dichotomous responses; where “yes” is scored as a “3” and a “no” requires answering an additional sub-question, “*Over the past week how much has your skin been a problem at work or studying*”. Responses for this sub-question range from “a lot” coded a “2”, to “not at all” coded a “0.” The DLQI is calculated by summing the response to each question; the maximum score is “30” and the minimum score is “0”. The higher the score, the lower the dermatologic quality of life. Guidelines for interpreting the index are that the dermatologic condition has: 0-1 = no effect at all on patient's life; 2-5 = small effect on patient's life; 6-10 = moderate effect on patient's life; 11-20 = very large effect on patient's life; 21-30 = extremely large effect on patient's life.

Social Anxiety. Symptoms of social anxiety will be assessed using the Liebowitz Social Anxiety Scale (Liebowitz, 1987), one of the most widely used scales to measure social anxiety. It consists of 24 items designed to assess fear and avoidance in different situations that are likely to produce social anxiety such as going to a party or speaking in public. For each situation, participants are first asked to state how fearful or anxious they feel in that situation using a Likert scale that ranges from “none” (0) to “severe” (3). Then they are asked to state how often they avoid that same situation using a Likert scale that ranges from “never” (0) to “usually” (3). Responses are summed to create an overall anxiety score. The scale is highly reliable ($\alpha > .70$) and has discriminant and convergent validity when administered by a clinician or through participant self-report (Cox, Ross, Swinson, & Drenfeld, 1998).

Depressive Symptomatology. We will assess depressive symptomatology using the Hospital Anxiety and Depression Scale (HADS) (Zigmond and Snaith 1983), one of the most widely used screening tools to identify symptoms of depression, anxiety and emotional distress amongst patients being treated for a variety of clinical problems. It consists of 14 items, 7 of which assess generalized symptoms of anxiety and the remaining 7 assess depressive symptomatology. Although the specific wording of the item responses vary in accordance to the item, all responses are coded using a Likert format ranging from “0” to “3” where the most positive response is coded a “0” and the most negative response a “3”. The maximum score for each subscale is 21; higher scores are reflective of more symptoms of anxiety or depression. HAD has good psychometric properties. It is internally consistent and has good reliability, convergence and discriminant validity (Herrmann 1997; Beck et al., 1997; Herrero et al., 2003; Whelan-Goodinson et al., 2009; www.abiebr.com/node/410 downloaded 8/15/2014).

Self-esteem will be assessed using the Rosenberg Self-Esteem Scale (Rosenberg, 1965), one of the most widely-used self-esteem measures in social science research. It consists of ten items designed to assess respondent's self-satisfaction, self-respect and other general feelings about himself/herself. The response format is a four point Likert scale ranging from “strongly agree” to “strongly disagree”. For items 1, 2, 4, 6, 7: Strongly Agree=3, Agree=2, Disagree=1, and Strongly Disagree=0. For items 3, 5, 8, 9, 10: Strongly Agree=0, Agree=1, Disagree=2, and Strongly Disagree=3. The scale ranges from 0-30, higher scores indicating higher self-esteem. The scale has been used extensively and across a number of different populations and it can be used as a unidimensional or a multi-dimensional scale with two factor-structures, self-confidence and self-deprecation. It has high test-retest reliability with estimates

ranging between .82 and .88 and Chronbach's alpha ranging between .77 and .88 (see Blascovich and Tomaka, 1993 and Rosenberg, 1986 for further detail).

K. Potential Risks to Participants

Some participants may experience postinflammatory hyperpigmentation, pain and burning sensation as a result of being treated with ALA-PDT, but these side-effects occur rarely and when they do they are typically associated with longer incubation periods of 3 hours or longer. To minimize this risk, we are proposing to use 1 hour incubation period, the shortest time possible to obtain the desired sensitization. Consequently, we consider the risk level for this concern is of low magnitude and duration. Individuals treated with ALA-PTA will experience short-term sensitivity to sunlight. This risk is minimized by the brief incubation period we selected and the careful instructions we will provide to participants regarding the need to protect themselves from exposure to sunlight. Thus, the risk is of low magnitude and duration.

Some participants may temporarily experience fatigue, nausea, sleepiness and flu-like symptoms 60 to 90 minutes after MCT, similar but slightly stronger than those that some people experience after a massage. Although these side-effects rarely occur, they are the by-product of the lymphatic system flushing toxins from the body and they resolve within 24 hours. To minimize this risk, we will strongly encourage participants to stay maximally hydrated to mitigate this side-effect. Thus, the risk is of low magnitude and duration.

Some participants may experience psychological distress from responding to some of the questions in our assessment battery. They may be sensitive about reporting their feelings regarding how acne affects their daily activities and social interactions or how sad, anxious or depressed they feel as a result. We have taken steps to minimize this risk by ensuring that our research staff is well trained and prepared to identify distress in our participants. Our staff will remind participants that they have the option of refusing to continue with the treatment or not answer any question that makes them feel uncomfortable or anxious. The risk level for this concern is of low magnitude and duration.

Another risk is the potential for a breach of confidentiality from study materials being accessed by non-authorized individuals or staff inadvertently divulging confidential information. The risk is minimized by our extensive staff training regarding confidentiality protections and the strict procedures we have in place to storing, de-identifying, and protecting all study materials. All study materials and data will be identified with a unique identification number not the participant's name and stored in password protected files and secure computers. Thus, this concern is of low magnitude and duration.

L. Potential Benefit of the Research to Participant and Others

While participating in this study may not directly benefit all participants, it is likely that some participants will experience improvement in their acne. The study has the potential to generate new knowledge that may be used for the treatment of a debilitating, prevalent condition. It will provide valuable information about safety and efficacy of using MCT in treating acne as well as preliminary evidence on the use of a new combination therapy ALA-PDT with MCT. Additional knowledge to be gained from this study derives from the use of psychosocial measures. Not only are we documenting the physiologic outcomes of treatment, but we will also be able to describe patients' reactions and feelings prior to, during and post treatment. Furthermore, if the results of this trial are promising, we will have the necessary preliminary evidence to launch a large efficacy scale trial of a new therapeutic treatment for acne.

M. Risk/Benefit Ratio

Based on the evaluation of the potential risks associated with this study, the steps we will take to minimize these risks, and the potential benefits to the individual and society, the risks seem reasonable in relation to the anticipated benefits stated above.

N. Consent Forms

Consent form is attached.

O. PHI

Because this study is being conducted in a clinical setting, it has PHI.

P. Qualification of Investigators

The CVs of Investigators are attached to this protocol.

Q. Timeline

Literature Cited

- [1] Elizabeth Uhlenhake, BS [name], & [name], PhD
Acne vulgaris and depression: a retrospective examination *Journal of Cosmetic Dermatology*, 9, 59–63
- [2] Gollnick H, Cunliffe W, Berson D, Dreno B, Finlay A, Leyden JJ, Shalita AR, Thiboutot D.
